in-person. Participants will be asked to sign the electronic consent form on Qualtrics or REDCap, mail a signed paper version back to the research assistant, or drop off a signed paper version to their clinic for research staff to pick up. Alternatively, consenting maybe be done in-person. Participants will also keep a copy of the consent for their records.

Participants randomized to the MORE condition will participate in eight, weekly, two-hour online group sessions led by a clinic or study counselor. Each session will contain 5 to 9 participants and will be conducted online through secure video or phone conferencing. If a participant is unable to join the MORE session through video conference due to technical difficulties at the time of the session, the participant will be instructed to join the session by phone or the participant may go to their clinic and a research or clinic staff member can help them access the intervention through their tablet or a computer. Attendance at each session and reasons for missing sessions will be recorded. Participants randomized to the control condition will continue receiving treatment as usual at their clinic.

All study participants will partake in a total of three interviews lasting up to 120 minutes occurring at baseline, 8-, and 16-weeks (week 1 will be considered the week of the first MORE group session) by video or phone conferencing or in-person. If more than 3 months since baseline survey was administered from start of group (study intervention), clients will be asked to do another baseline survey. Each participant will also have a urine or saliva sample collected during each assessment. This is required to verify self-report of drug use. Due to social desirability, it is common for people to not accurately report drug use; therefore, biochemical verification is the gold standard measure of drug use. Participants will be mailed a urine or saliva test prior to the interview.

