All study participants will participate in three video, phone conferencing, or in-person visits at baseline, 8-, and 16-weeks. Information will be collected on demographic characteristics, substance use, methadone treatment, opioid craving and withdrawal, physical pain, non-reactivity, negative and positive affect, attentional bias, cognitive and

Version Number: 15, 2/2/2022 Protocol Number: Pro20190016877 PI Name: [name]

Protocol Title: Mindfulness Oriented Recovery Enhancement (MORE) as an Adjunct to Methadone Treatment RESERVED FOR IRB STAMP
DO NOT MODIFY THIS SPACE

mental health, physical health, and intervention implementation and attitudes. At the baseline and 8-week research visits, participants will complete three cognitive tasks on a computer or tablet that assess inhibitory control, implicit (automatic) associations, and the precedence of global features in visual perception. Urine and/or saliva samples will be requested at each assessment for confirmation of self-reported drug use or recent drug test results will be obtained from the participants' clinic chart. In addition, participants will partake in daily ecological momentary assessments (EMA) throughout the 16-weeks of study participation that include brief measures of pain intensity, mood, and substance use. Participants will also be asked to initiate communication via smartphone, computer, or tablet when they either lapse to opioid use or experience serious craving. Self-initiated responses will include information about the circumstances surrounding their craving/lapse. A synopsis of all study instruments are included below (see 1.98 – Study instruments).

C. Define the duration of the study and the length of time each subject will participate in the study. This study is expected to take two years. Each subject will participate in the study for a total of 16-weeks.

- **D.** Describe any primary and secondary study or safety endpoints
 - Primary Outcome: time until opioid relapse
 - Secondary Outcomes: opioid abstinence, days of drug use, MMT adherence, craving, pain symptoms, and emotional distress

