1.8 Primary Specimen Collection

A. What types of specimen will be collected, where, and by whom?

We will utilize a urine or saliva screen that tests for buprenorphine and methadone (to provide corroboration of MAT engagement and compliance) and additional substances (e.g., benzodiazepines, barbiturates, cocaine, marijuana, methamphetamine, morphine, oxycodone, phencyclidine and amphetamine). These specimens will be collected at baseline and each follow-up time point (8- and 16-weeks). Biochemical verification of self-report opioid relapse and other drug use is the gold standard measurement of drug use and, without biochemical verification, self-reported drug use as an outcome variable will be questioned by the scientific community. Participants will be mailed a urine or saliva test prior to the interview. Alternatively, the patient can pick up urine or saliva test at their respective clinic. If feasible, drug screen may be done in-person. At the time of the interview, participants will be instructed on how to administer the test and will be instructed to show the research assistant the results on the video conference. The research assistant will then record the results. If participants are unable or unwilling to attend a video research appointment, a research assistant will conduct an interview over the phone and participant will self-report the drug screen results. The fact that drug screen results are self-reported will be noted. Alternatively, if feasible, the drug screen may be done in-person. All results (positive or negative) be will be recorded in the research database that will only be identified with participant's study ID and not the participant's name. Drug test results will not be shared with anyone, including the participant's clinic, without written consent from the participant. With participant consent, the results of the most recent drug tests conducted by the patients' clinics may be obtained from the patients' charts.

8

B. How will the specimens be transported and by whom?

Version Number: 15, 2/2/2022 Protocol Number: Pro20190016877 PI Name: [name]

Protocol Title: Mindfulness Oriented Recovery Enhancement (MORE) as an Adjunct to Methadone Treatment RESERVED FOR IRB STAMP DO NOT MODIFY THIS SPACE

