1.9 Interviews, Focus Groups, or Surveys

A. Administration

Timing and Frequency

Research staff will collect interview data and drug screens from both intervention and control group subjects through video, phone interview, or in-person using standardized measures conducted at baseline and 8- and 16-weeks. Cognitive testing data will be collected at baseline and 8-weeks. If the research assessments are conducted over the phone, drug screen results will be recorded as self-reported. Additionally, subjects will engage in twice-daily EMA assessments of approximately 3-5 minutes each for 16-weeks. For 16-weeks, subjects will also initiate EMA communications to report lapses or serious cravings, which will also last for under 5 minutes. For those who do not complete their EMA, our research staff will do a timeline follow-back over the phone or video conferencing to collect missing EMA drug use data. EMA completion reports will be reviewed, weekly, and participants will be contacted, as needed, to collect missing daily drug use data.

Location

The assessments and drug screens will take place via video/online, phone interview, at their clinic, or at another safe and private location in the community (e.g., library, park, or coffee shop).

Procedures for Audio and Visual Recording

Audio or video recordings will be made of the MORE therapy sessions. All recordings will be stored in password protected computers, in a locked office at [name], or in password protected files, on the Rutgers network or HIPAA compliant Box file.

9

B. Study Instruments

Version Number: 15, 2/2/2022 Protocol Number: Pro20190016877 PI Name: [name]

Protocol Title: Mindfulness Oriented Recovery Enhancement (MORE) as an Adjunct to Methadone Treatment RESERVED FOR IRB STAMP
DO NOT MODIFY THIS SPACE

- Time until first opioid lapse assessed through ecological momentary assessment data and timeline follow-back.
- Time until MMT dropout assessed through clinic records (abstracted by the study counselor who will have access to the clinic records). Time until dropout will be calculated from enrollment until last dose of methadone.
- Total days of methadone treatment assessed through clinic records (abstracted by the study counselor who will
 have access to the clinic records). Number of days will be calculated from enrollment until each follow-up timepoint.
- Total days of opioid or any drug use assessed through EMA data and timeline follow-back

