- Trajectories of positive and negative affect assessed through Positive and Negative Affect Schedule.
- Drug craving assessed with an adapted version of the Penn Alcohol Rating Scale.
- Pain severity and pain interference assessed with the Brief Pain Inventory and the Gracely Pain scale⁷

Assessment of additional secondary outcome and other relevant measures that could mediate or moderate outcomes are described below:

Ecological Momentary Assessmenet (EMA) data collection (ongoing from baseline to 16 weeks). The EMA and other survey data will be programmed as a REDCap or Qualtrics survey delivered over a password-protected smart phone, computer, or tablet that will not store any data. REDCap and Qualtrics are secure, HIPPA-compliant, webbased application for building and managing online surveys and databases. The EMA survey approach will involve 1) collecting event-contingent records of lapses when they occur as well as 2) regular random assessments, prompted by random text messages initiated by Twilio, 3x daily via smartphones. For event-contingent records, participants will be asked to initiate an entry when an opioid lapse or opioid craving without use occurs, and note how they were feeling and the extent of craving. One random assessment probe will be scheduled early in the day and one will be scheduled in the evening. The random probes will be generated by an algorithm in REDCap or Qualtrics and linked to a Twilio phone number. For random assessments, participants will be asked to note how they are feeling, drug use, and whether they completed their homework (if in the intervention group). Research staff will demonstrate to study participants how to use the phones/tablets, respond to the prompts, and provide event contingent data. Research staff will provide instructions about how to use the phone/tablet and practice using the phone/tablet with participants until they are capable of using it.

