Hypothesis 1.1. (**Primary Outcome**) MORE will result in longer duration of time to first opioid lapse and MMT dropout than TAU. We will use survival analysis (Kaplan Meier curves and marginal model analysis for multivariate survival data)³⁴ to test effects of MORE vs. TAU on time until first opioid lapse and MMT dropout—evidenced either on EMA, Timeline Follow-Back, urinalysis or medical records (whichever is first). Survival analysis will be run once, at 16 weeks post-baseline. Clustering within cohort will be adjusted in the multivariate marginal model analysis.³⁴ We will estimate the hazard ratios of opioid lapse and MMT dropout when comparing MORE with TAU, controlling for covariates.

Hypotheses 1.2 and 1.3 (Secondary Outcomes). MORE will result in more days of opioid abstinence (or less days of use) and a higher rate of biochemically-verified abstinence over time than TAU. Generalized linear mixed model (GLMM)³⁵ repeated measures analysis will be used. Specifically, identity link will be used for "number of abstinent days" as the dependent variable, and logit link will be used for "opioid abstinence (yes/no via urinalysis)" as the dependent variable. Days of use/abstinence will be assessed via EMA, number of drug use days since last visit and past 30 days, and the Timeline Follow-Back. In cases of conflicting findings across data sources, we will assume the highest number of days of use or lowest number of abstinent days recorded for that period. Analyses will include group (MORE vs. TAU), time, and group by time interactions as the fixed effects independent variables. Correlations among repeated measures and among subjects within cohorts will be modeled using nested random effects. Potential confounders that meet the p<0.10 criterion stated above will be entered as covariates. Linear contrasts will be constructed to test between-group differences in "days of use" or "days of abstinence" separately at each timepoint. In comparing days of use, if a substantial proportion of subjects do not use opioids, resulting in excessive zero days of use, we will use a two-part logistic/linear analysis model.^{36,37}

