Exploratory, temporally-dynamic analysis of the effects of mindfulness practice on EMA measures of craving, affect, and pain. Growth curve analyses and multivariate autoregressive latent trajectory analyses (m-ALT) of EMA data will examine antecedents and consequences of drug use as well as the impact of skill practice on craving and drug use. EMA data will yield granular analyses of process variables (mindfulness, reappraisal, and savoring practice) and quantify how skill use dynamically co-varies with pain, craving, and drug use during and after treatment. Lagged growth curve analyses⁴¹ will examine treatment and practice effects on: A) trajectories of positive/negative affect, craving, and pain; B) relationships among these variables over time; and C) how trajectories in affect, craving, and pain predict drug use in separate m-ALT models. The models, like ones published by [name], will estimate cross-lagged and autoregressive effects, as well as latent intercept and growth factors, among EMA variables, conditioned on a treatment group variable and measures of mindfulness, reappraisal, and savoring practice. EMA models will be corrected for multiple comparisons.

AIM 3 Analyses. To test gender as a moderator of treatment response, we will include all main effects and all two-way, and three-way interactions of gender, treatment, and time in GLMM analysis models, and all main effects and the two-way interaction of gender and treatment in the marginal multivariate survival analysis models. A significant gender x treatment x time interaction in GLMM models, tested by F test, indicates that treatment effect on changes in outcomes over time differ by gender. A significant gender x treatment interaction in survival models, tested by Wald test, indicates that treatment effect on time to event differs by gender. In GLMM analysis, gender differences on outcomes at 8, 16, 24, and 52 weeks will be estimated and tested using linear contrasts. Other potential moderators (e.g., race, income, mental health, trauma, and MMT phase) will be explored using similar approaches as exploratory analyses.

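### The gender contrasts are planned at 24 and 52 weeks although data collection ends at 16 weeks, and as worded those at 8 and 16 weeks compare genders rather than the MORE-minus-TAU effect between genders

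*Combined protocol and SAP*

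**What the plan says.** Section 1.1 B hypothesises that gender moderates treatment response. It is the only moderator with a stated hypothesis; race, income, mental health, trauma and MMT phase are exploratory. Section 1.1 A lists moderators as Aim 4, while the analysis stands in Section 6.1 A under the label Aim 3.

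That paragraph does two things. First, it defines formal tests: a three-way interaction of gender, treatment and time in the GLMM (F test) and a two-way interaction of gender and treatment in the survival models (Wald test). It explains that each shows whether the treatment effect differs by gender. Second, it adds that in the GLMM "gender differences on outcomes at 8, 16, 24, and 52 weeks will be estimated and tested using linear contrasts". The other moderators are to be handled in a similar way.

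The schedule is given elsewhere:

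- Section 1.3 C: "Each subject will participate in the study for a total of 16-weeks".
- Section 1.3 A: "three interviews lasting up to 120 minutes occurring at baseline, 8-, and 16-weeks".
- Section 1.9 B, on chart-derived days of methadone treatment: "Number of days will be calculated from enrollment until each follow-up timepoint".
- Section 6.1 A, on the primary outcome: "Survival analysis will be run once, at 16 weeks post-baseline".

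**The concern.** There are two separate faults in the sentence on contrasts.

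It names timepoints at which nobody is assessed. An analyst following the plan would have to depart from it for weeks 24 and 52, or report model extrapolations as if they were results.

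It also names the wrong quantity. Moderation means that the MORE-minus-TAU difference is not the same in women and men. A gender difference in the outcome is a different parameter, and one estimated with better precision. If it is reported under the moderator aim, a gender main effect could be taken as evidence of moderation. If the sentence is left as it is, the quantity to be estimated at weeks 8 and 16 will be chosen after the data are in.

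**Working it through.** The plan gives no sample size or power figure for the moderator analysis, so there is no figure to reproduce. The check compares schedules and then works through the contrast.

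**Timepoints against data.** Contrasts are planned at weeks 8, 16, 24 and 52. The sources of data run as follows:

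- interviews: baseline, 8 and 16 weeks (Sections 1.3 A and B, 1.9 A)
- drug screens: baseline, 8 and 16 weeks (Sections 1.8 A, 1.9 B)
- EMA: baseline to 16 weeks (Section 1.9 B)
- days of methadone treatment from charts: counted to the follow-up timepoints, that is 8 and 16 weeks (Section 1.9 B)
- survival analysis: 16 weeks (Section 6.1 A)

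Weeks 24 and 52 therefore lie 24 − 16 = 8 and 52 − 16 = 36 weeks after the last visit. If time is categorical, these contrasts cannot be estimated. If time is linear, they are extrapolations of 8/16 = 0.5 and 36/16 = 2.25 times the observed span beyond its end.

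**Calendar.** Accrual is 1.5 years, about 78 weeks (Section 6.1 B), in a study of two years, about 104 weeks (Section 1.3 C). Then 78 + 16 = 94 and 78 + 24 = 102 fit, but 78 + 52 = 130 does not. Week 52 could not be reached for the whole sample even if a visit were added.

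**What the contrast measures.** At one visit, write W and M for women and men, with subscripts for arm.

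- Gender difference pooled over arms: G = (W_MORE + W_TAU)/2 − (M_MORE + M_TAU)/2
- Moderation: D = (W_MORE − W_TAU) − (M_MORE − M_TAU)

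Two sets of invented means show that G and D are unrelated:

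- Women 8 (MORE) and 3 (TAU), men 5 and 0: G = 5.5 − 2.5 = 3, D = 5 − 5 = 0.
- Women 3 and 0, men 0 and 3: G = 1.5 − 1.5 = 0, D = 3 − (−3) = 6.

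**Precision.** With SD σ, 1:1 allocation within each gender, and n_W women and n_M men in total:

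- Var(G) = σ²(1/n_W + 1/n_M)
- Var(D) = σ²[2/(n_W/2) + 2/(n_M/2)] = 4σ²(1/n_W + 1/n_M)

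So SE(D) is twice SE(G) at any gender split. Take N = 184 (Section 4.5), two-sided 5% and 80% power (multiplier 1.96 + 0.84 = 2.80). Assume σ = 1, no attrition and no clustering. The share of women is not given and is also assumed:

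- 50% women: SE(G) = 0.147 and SE(D) = 0.295; detectable differences 0.41 SD and 0.83 SD.
- 30% women: SE(G) = 0.161 and SE(D) = 0.322; detectable differences 0.45 SD and 0.90 SD.

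**The case against.** The strongest reply is that the moderator question is already answered before the disputed sentence begins. The paragraph opens by stating that gender is tested as a moderator, fits all the interactions, and says what a significant interaction means. Both interaction tests need only the baseline, 8- and 16-week data, or the 16-week survival data. The phrase about gender differences may then be shorthand for following up the three-way interaction, or a descriptive supplement.

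Most of this stands. A reader might infer that the moderator aim cannot be carried out, or that moderation goes untested. The documents do not support either reading, because the F and Wald tests are specified and can be run.

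The reply does not rescue the contrasts. No reading supplies data at 24 or 52 weeks. As for the wording, even if gender differences were taken within each arm, moderation would be the difference between those two differences, and the plan does not say to form it. For Hypotheses 1.2 and 1.3, the same section does say plainly that its timepoint contrasts are differences between the treatment groups, so equal clarity is possible here.

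A reader might also infer a multiplicity cost, with a Holm family of four tests instead of two. The documents do not support that. Section 6.1 A applies Bonferroni-Holm to outcome analyses without defining a family made of these contrasts, and a contrast that cannot be estimated yields no p-value to enter.

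**Conclusion.** The point holds for the timepoint contrasts only. Two of the four have no data, which is a plain internal contradiction in the current text. The other two, read literally, do not measure moderation; that part rests on the wording, which may be loose drafting. The same fault carries over to the exploratory moderators, because they are to be analysed in a similar way.

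The primary analysis, the secondary treatment comparisons and the formal interaction tests are unaffected. The doubling of the standard error assumes 1:1 allocation within gender and equal variances. The detectable differences also rest on the assumed SD, gender split, full retention and absence of clustering, and serve only to show scale. The 24- and 52-week timepoints may be left over from a design with longer follow-up, but the documents do not say so.

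**What to change.** Replace the sentence on gender contrasts with one to this effect: *As follow-up to the gender-by-treatment-by-time interaction test, the between-gender difference in the MORE-minus-TAU effect will be estimated with a confidence interval at weeks 8 and 16, using linear contrasts from the same model (on the link scale for binary outcomes).* State that the exploratory moderators use the same form of contrast, and align the aim number with Section 1.1.

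The cost is a one-sentence amendment plus the renumbering. It needs no new data, visits or participants. If gender differences in outcomes are also wanted, they can be kept as description and labelled as such.

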1.5 Sample Size Justification

With 1.5 years of subject accrual and an additional follow-up of 16 weeks after the accrual interval, our study needs 47 subjects per group to test a hazard ratio of 0.55 when comparing MORE to TAU, with 80% power and alpha=5% (two-sided). To account for attrition, we will recruit up to 92 subjects per group (a total of 184 subjects at a 1:1 ratio for MORE vs. TAU).

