C11. Outcomes and Future Directions. We expect to establish the efficacy of an innovative intervention that can enhance MAT by supporting chronic pain management and MMT adherence while preventing drug use and opioid relapse. Results from this study will inform the development of services in New Jersey and other states seeking efficacious strategies to combat the opioid epidemic. If this study demonstrates MORE's efficacy as an adjunct to MMT, we will follow this study with a Stage IV implementation/dissemination study to enhance the rapidity and fidelity of uptake of the intervention into standard of care for persons with OUD.

B. Provide a power analysis. (As applicable, e.g. quantitative research)

We powered the R33 study based on data from prior research. We used a study of an MBI for substance users,⁴ which showed that the hazard ratio of relapse to drug use for the intervention compared to TAU was 0.46. We thus assumed a similar, but more conservative hazard ratio of relapse to opioid use of MORE compared to TAU at about 0.55. (We are using a slightly more conservative hazard ratio than in the original application due to the increased power obtained by reducing the number of treatment conditions from three to two.) We also assumed that the median relapse time to opioid use is 99 days, based on a prior study of relapse to drug use in a general MMT population.⁵ With 1.5 years of subject accrual and an additional follow-up of 16 weeks after the accrual interval, our study needs 47 subjects per group to test a hazard ratio of 0.55 when comparing MORE to TAU, with 80% power and alpha=5% (two-sided). To account for attrition, we will recruit 85 subjects per group (a total of 184 subjects at a 1:1 ratio for MORE vs. TAU).

Version Number: 15, 2/2/2022 Protocol Number: Pro20190016877

PI Name: [name]
Protocol Title: Mindfulness Oriented
Recovery Enhancement (MORE) as an
Adjunct to Methadone Treatment

RESERVED FOR IRB STAMP DO NOT MODIFY THIS SPACE

C. Describe the steps that will be taken secure the data (e.g., training, authorization of access, password protection, encryption, physical controls, certificates of confidentiality, and separation of identifiers and data) during storage, use, and transmission.

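### The 47-per-group sample size counts follow-up that the trial does not collect; on 16 weeks per participant, 47 per group gives 49% to 65% power, not 80%

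*Combined protocol and SAP*

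**What the plan says.** Sections 1.5 and 6.1 B give the same basis: "With 1.5 years of subject accrual and an additional follow-up of 16 weeks after the accrual interval, our study needs 47 subjects per group", for a hazard ratio of 0.55 with 80% power and two-sided alpha of 5%. Section 6.1 B adds the event-time assumption: "We also assumed that the median relapse time to opioid use is 99 days". It takes this from a study in a general methadone population and does not say which arm it describes.

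Both sections then raise recruitment to allow for attrition. Section 1.5 says up to 92 per group, 184 in all. Section 6.1 B says 85 per group but also 184 in all. Section 4.5 A gives up to 184. No attrition rate is stated.

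On follow-up, Section 1.3 C says: "Each subject will participate in the study for a total of 16-weeks". Assessments are at baseline, 8 and 16 weeks, and the EMA window in 1.9 B also ends at 16 weeks. For the primary outcome, 6.1 A (Hypothesis 1.1) says: "Survival analysis will be run once, at 16 weeks post-baseline". It continues: "Clustering within cohort will be adjusted in the multivariate marginal model analysis". The only later time points are in the moderator analysis, where "gender differences on outcomes at 8, 16, 24, and 52 weeks will be estimated and tested using linear contrasts". Those contrasts belong to the mixed models, and no 24- or 52-week visit is planned.

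**The concern.** The power of a log-rank or Cox comparison depends on the number of events. Accrual time adds events only if participants stay under observation until a common closing date. Here each participant leaves at 16 weeks whatever the entry date, so the 1.5 years of accrual adds no person-time per participant. If 47 was computed with that extra person-time, the expected number of events is too high and the required sample size too low.

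Two things depend on it. One is the stated power for the primary outcome. The other is the attrition allowance: needing 47 and recruiting 92 implies that 1 − 47/92 = 49% of participants could be lost with 80% power kept. A reader who relies on that reserve could be too relaxed about loss, or read too much into a null result.

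**Working it through.** **Inputs.** From 6.1 B: hazard ratio 0.55, two-sided alpha 5%, power 80%, 1:1 allocation, median 99 days, accrual 1.5 years (548 days) plus 16 weeks (112 days). From 1.3 C and 6.1 A: 112 days per participant. Assumptions: exponential event times, uniform accrual, no clustering allowance. As the arm is not named, the 99 days is read three ways: as the TAU median, as the pooled median (which gives a TAU median of 74.4 days and a MORE median of 135.3 days), or as the MORE median (TAU median 54.5 days).

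**Events needed (Schoenfeld).** 4 × (1.960 + 0.842)² / (ln 0.55)² = 87.8. Freedman's formula gives 93.1. With 47 per group the event proportion must be 87.8/94 = 93%.

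**The plan's own figure.** With uniform accrual over A = 548 days and F = 112 days to a common close, for hazard λ,

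P(event) = 1 − [exp(−λF) − exp(−λ(A+F))] / (λA).

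The number per group is 87.8 / (2 × mean P). This gives 54.5 (TAU), 50.4 (pooled) and 47.5 (MORE). The MORE reading reproduces 47 to within rounding, with 79.6% power. If everyone were followed for the full 660 days, the results would be 46.0, 44.7 and 44.1. So 47 is approached only with follow-up that runs well past 16 weeks.

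**The trial's actual follow-up.** P(event) = 1 − exp(−112λ). Power = Φ(½√d × |ln 0.55| − 1.960), where d is the expected number of events.

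| 99 days is the median of | TAU | pooled | MORE |
|---|---|---|---|
| P(event), TAU arm | 0.543 | 0.648 | 0.760 |
| P(event), MORE arm | 0.350 | 0.437 | 0.543 |
| Mean P(event) | 0.447 | 0.542 | 0.652 |
| Events with 94 participants | 42 | 51 | 61 |
| **Power, 47 per group** | **49%** | **57%** | **65%** |
| Evaluable per group for 80% (Schoenfeld) | 98.3 | 81.0 | 67.4 |
| Same, Freedman | 104.2 | 85.9 | 71.5 |
| Power, 85 per group, no loss | 74% | 82% | 88% |
| Power, 92 per group, no loss | 77% | 85% | 90.5% |

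Log-rank simulation agrees. At 47 per group (20,000 runs) it gives 48.5% (TAU) and 64.6% (MORE). At 92 per group (5,000 runs) it gives 76.9% and 91.2%.

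**Loss that 184 can absorb at 80% power.** If lost participants contribute nothing, the limit is 1 − 87.8/(184 × mean P): none, 12% and 27%. If they drop out at a constant rate and are censored at that point, it is none, 26% and 56%. At 19% loss (an assumption, taken from the 81% retention in the pilot described in 1.4), power is 68%, 77% and 84% with no contribution, and 73.5%, 81% and 88% with censoring. For the TAU reading with censoring, simulation gave 71.7%.

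**Can 47 be rescued?** It reaches 80% on 112 days only if the TAU median is about 19.5 days or less. If the clock began at a baseline 91 days before the first session (203 days in all, an upper bound), power is 65%, 71% and 76%. If methadone dropout also counted as an event (assuming 50% by 12 months in TAU, after 1.2, and the same hazard ratio), power is 56%, 62% and 68%.

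**Recruitment figures.** 2 × 85 = 170, not 184; 2 × 92 = 184.

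**The case against.** The strongest reply is that the trial does not plan to stop at 47 per group. With 184 participants and no loss, power exceeds 80% under two of the three readings, and under the TAU reading as well (84%) if methadone dropout counts as an event. Under staggered accrual, the reading that best reproduces 47 is the MORE one, which gives the 65% end of the range rather than 49%. Under that reading, with dropouts censored rather than discarded, 184 participants with 49% loss still give 82% power, so the implied reserve is real. Missing drug-use data are also to be recovered by timeline follow-back, which makes the no-contribution model harsh. Finally, the plan sets no numeric retention target, so no formal decision depends on the 49%.

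These points stand, and they limit the consequence. They do not rescue the statement itself, because 47 per group falls short of 80% under every reading. The reserve also fails under the other two readings: with 49% censored loss, 184 participants give 65% (TAU) and 74% (pooled). The stated source of the median, a general methadone population, fits the TAU arm best. On that reading, with relapse alone as the event, 184 participants miss 80% before anyone is lost. The composite event is uncertain support, since 6.1 B powers relapse to opioid use and 6.1 A estimates separate hazard ratios for lapse and dropout.

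**Conclusion.** The statement that 47 per group gives 80% power is wrong as written in both sections. On the 112 days of follow-up that the trial collects, 47 per group gives 49% to 65%, and 80% needs about 67 to 98 evaluable participants per group, depending on which arm the 99-day median describes. The cause is the follow-up assumption: the stated accrual design gives 47.5 per group under the MORE reading, and no reading gives 47 on 112 days.

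The planned 184 gives 77% to 90.5% before loss. Whether the trial is adequately powered therefore turns on inputs the plan leaves unstated: the arm, the event and the loss model. The figures assume exponential times and make no allowance for cohort clustering or the Bonferroni-Holm adjustment; such an allowance would generally lower power further. The 85-per-group figure in 6.1 B is a separate arithmetic inconsistency.

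**What to change.** In 1.5 and 6.1 B:

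1. Delete the 47-per-group requirement and its accrual-plus-follow-up basis.
2. Recompute on 112 days of follow-up per participant.
3. Name the arm to which the 99-day median applies, and say whether methadone dropout counts as an event in the powered endpoint.
4. State the attrition rate, how loss is modelled, and whether cohort clustering is allowed for.
5. Restate power for up to 184 participants on those assumptions.
6. Reconcile 85 with 92 per group.

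Possible wording, if 99 days is the TAU median:

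> Each participant is followed for 112 days. For a hazard ratio of 0.55, two-sided alpha 5%, exponential times and a TAU median of 99 days, 88 events give 80% power. Up to 184 participants (92 per group) give about 82 events and 77% power with no loss. At an assumed 19% loss, power is about 68% if lost participants contribute nothing and about 72% to 74% if they are censored at dropout, before any allowance for cohort clustering.

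The no-loss figure becomes 85% if the median is pooled and 90.5% if it is the MORE median. The 19% should be replaced by the sponsor's own expected rate.

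The cost is one recalculation and changes of wording. No added enrolment is required. Under the TAU reading the stated power becomes less favourable, and the apparent attrition reserve disappears.
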